7.4.6 Selection and timing of doses for each patient

Upon completion of the screening assessments and confirmation of patient eligibility, including confirmation of sulfamidase enzymatic activity, patients are assigned a subject number and allocated to a dose cohort in strict consecutive order.

At the time of the first SOBI003 infusion, the patient should not have clinically significant evidence of ongoing infection, as judged by the investigator, or ongoing treatment with antibiotics. In such cases, the first infusion should be postponed until the infection has resolved.

SOBI003 is administered as 4-hour i.v. infusions given once weekly for a duration of 24 weeks. The infusions are administered by qualified health care professionals. Every effort should be made to have the infusions administered every 7th day. A +/- 1-day window is applied after the 4th infusion. Therefore, if the first infusion was administered for instance on a Wednesday, then the 5th to the 24th infusions can be administered on Tuesdays, Wednesdays or Thursdays.

In case of signs and/or symptoms of ongoing infection at subsequent infusion occasions, infusion may be postponed, as judged by the investigator. If the infusion needs to be postponed more than 3 days, then the investigator should discuss with the Sponsor's MD to determine the timing of the next infusion (i.e., whether to await the next scheduled infusion).

Within 30 to 60 minutes prior to each infusion, a single dose of a non-sedative antihistamine should be administered. The antihistamine can either be e.g., cetirizine, levo-cetirizine, loratadine, des-loratadine or fexofenadine, and the administered doses will be in compliance with locally approved labeling. The antihistamine agent is selected at the discretion of the investigator. Antipyretic medication may also be administered, at the discretion of the investigator.

The actual doses of SOBI003 to be administered should be based on the patient's bodyweight at 4-week intervals (i.e., the actual dose administered at Weeks 1 to 4 is based on the bodyweight obtained pre-infusion at Week 1, the actual dose administered at Weeks 5 to 8 is based on the bodyweight obtained pre-infusion at Week 5, etc.). The body weight is obtained either on the day prior to the infusion or the day of infusion.

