- k Use of general anesthesia or sedation is per local hospital routine and anesthesiologist judgement, as well as selection of anesthetic/sedative agents. If all Baseline procedures are not completed in one session, then local hospital routine determines minimum time between consecutive anesthetic/sedation episodes.
- l The port should be inserted at least 2 weeks prior to first SOBI003 infusion.
- m Only applicable when separate consent has been provided for future research. At Week 22, blood is collected for future genetic research. At Baseline and Week 22, blood and urine are collected for future biomarker research. CSF is collected at Baseline and Week 24 for future biomarker research. In case of Early Termination of SOBI003 treatment, blood and urine is collected for storage for future biomarker and genetic research.
- n Central laboratory analyses of sulfamidase activity in leucocytes.
- o Sampling time points:
 - Weeks 1 to 3: pre-infusion (Day 1) and Day 3. For patients <15 kg body weight, blood sampling on Day 3 at Week 3 is NOT applicable.
 - Weeks 4 to 8: pre-infusion.
 - Weeks 10 to 22: biweekly pre-infusion, i.e., Weeks 10, 12, 14 etc.
 - Week 24: Day 3.
- p Blood sampling for only hsCRP, IL-1ra, TNF α , IgE, and tryptase. Baseline sample analyzed only in case acute infusion/anaphylactic reaction occur during SOBI003 treatment to facilitate the determination of reaction etiology.
- q Frequent PK blood sampling is conducted at Weeks 1, 4, 12, and 24. Samples are also collected before start of infusion and at completion of the infusion at weeks 2, 3 and 8. PK blood sampling will be adjusted based on the patient's bodyweight in order not to exceed blood draw volume limits. At Baseline, the PK and immunogenicity samples should be taken on the day of CSF sampling for HS analysis. Details on PK blood sampling are given in Table 6.
- r Sleep pattern is assessed by actigraph recordings for 7 consecutive days at Baseline and at Weeks 11-12 and 23-24, i.e., Baseline assessment should preferably be completed prior to any anesthetic/sedation is applied and prior to PK and HS blood samplings. At Weeks 11 and 23, the aim should be to have the recordings completed prior to the SOBI003 infusions on Day 1 at Weeks 12 and 24. A sleep diary is completed during the days of actigraphy. Parents should complete the CSHQ upon completion of each actigraph assessment (i.e., at Weeks 12 and 24 this will be during the infusion days).

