On Day 1 (prior to start of infusion) of Week 8, blood is collected for immunogenicity and HS assessments and urine is collected for analysis of HS.

On Day 1 of Weeks 6 and 8, 12-lead ECGs are obtained within an hour of completion of the 4-hour infusion.

The patient may be discharged from the hospital 48 hours after start of each infusion.

7.5.1.9 Weeks 9 to 11

SOBI003 is administered as weekly infusions; a +/- 1-day window is applied. The patients will return to the hospital the day prior to or on the day of each infusion. Adverse events and use of concomitant medications during non-hospital stay are captured. Prior to start of each infusion, vital signs and general appearance and skin are assessed. At Week 9, body weight is also assessed to determine the SOBI003 dose to be administered at Weeks 9 to 12. The body weight is obtained either on the day prior to the infusion or the day of infusion. Within 30 to 60 minutes prior to start of each SOBI003 infusion, a single dose of an oral non-sedative antihistamine is administered.

Prior to start of infusion at Week 10, blood and urine is collected for safety laboratory analyses. SOBI003 is administered in accordance with Section 7.4.6.

Vital signs (including oxygen saturation) are assessed at approximately 2 hours after start of infusion as well as within an hour of completion of the infusion.

Within an hour of completion of the 4-hour infusion, general appearance and skin are assessed.

Prior to discharge at Week 10, the parent/caregiver is given the actigraph and the accompanying diary. The parent/caregiver is instructed to start the sleep assessment 7 days prior to attendance for the 12th infusion.

The patient may be discharged from the hospital 12 hours after start of each infusion.

7.5.1.10 Week 12

SOBI003 is administered as weekly infusions; a +/- 1-day window is applied. The patients will return to the hospital the day prior to or on the day of each infusion. Adverse events and use of concomitant medications during non-hospital stay are captured. The actigraph and accompanying diary are collected.

Prior to start of the infusion, the following is performed:

- Vital signs and a 12-lead ECG is obtained
- General appearance and skin are assessed
- Blood is obtained for immunogenicity, HS and PK assessments
- Urine is collected for HS analysis
- Blood and urine is collected for safety laboratory analyses

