Prior to start of each infusion, vital signs and general appearance and skin are assessed. At Weeks 17 and 21, body weight is also assessed to determine the SOBI003 dose to be administered at Weeks 17 to 20 and 21 to 24, respectively. The body weight is obtained either on the day prior to the infusion or the day of infusion. Within 30 to 60 minutes prior to start of each SOBI003 infusion, a single dose of an oral non-sedative antihistamine is administered.

Biweekly, prior to start of each infusion (i.e., at Weeks 14, 16, 18, 20, and 22), blood and urine is collected for safety laboratory analyses. At Week 22, for patients for whom separate informed consent has been provided for future research, blood and urine is collected and sent for storage at the central laboratory.

On Day 1 of Week 13, a PK blood sample is collected prior to start of infusion. SOBI003 is administered in accordance with Section 7.4.6.

Vital signs are assessed approximately 2 hours after start of infusion. Within an hour of completion of the 4-hour infusion, vital signs and general appearance and skin are assessed.

Prior to discharge at Week 22, the parent/caregiver is given the actigraph and the accompanying diary. The parent/caregiver is instructed to start the sleep assessment 7 days prior to attendance for the 24th infusion.

The patient may be discharged from the hospital 12 hours after start of each infusion.

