7.5.4.5 Sleep pattern

The patients' sleep pattern is evaluated using the CSHQ and by use of actigraphy.

Two additional items are added to the original CSHQ questionnaire to further characterize common MPS IIIA specific issues with sleep, i.e., disruptive behavior at night and dangerous behavior at night. The CSHQ is completed by the primary caregiver at Baseline and prior to the infusions at Weeks 12 and 24. This CSHQ will capture the child's sleep habits during the past week. Every effort will be made to have the same caregiver completing the CSHQ at each assessment time point.

An actigraph (ActiGraph GT9X Link) will be applied to the non-dominant wrist or ankle and recordings will be made for 7 consecutive days and nights at Baseline and at Weeks 11 and 23. The wrist or ankle placement should be used consistently throughout the study. At Baseline, the aim should be to have the recording completed prior to any anesthesia/sedation is applied and prior to blood samplings. At Weeks 11 and 23, the aim should be to have the recordings completed prior to the SOBI003 infusions on Day 1 at Weeks 12 and 24.

The device will be worn constantly during the recording periods only allowing removal for washing and bathing. The aim is to ensure that at least 5 days of evaluable recordings are obtained on each occasion. A daily wear time of 20 hours per day will be regarded as a compliant recording. The recording will be supported by an actigraph log. Recorded actigraph data will be evaluated using the accompanying software developed by the manufacturer. A subset of the actigraphy data is coded to be analyzed in a subsequent separate blinded analysis of the manually edited dataset.

The following parameters will be determined on the basis of recordings in the actigraph log:

- Bedtime (Clock time child is put to bed)
- Wake time (Clock time of child is taken out of bed)
- Time in bed (Time between Bedtime and Wake time)

The following variables are derived as obtained from the actigraph software:

- Sleep onset (Clock time for first appearance of a predetermined number of consecutive min of sleep)
- Sleep offset (Clock time for last of a predetermined number of consecutive min of sleep)
- Sleep period (Time between sleep onset and sleep offset)
- Total sleep time (TST, Duration of sleep in sleep period)
- Wake after sleep onset (WASO, number of minutes scored as wake during sleep period)
- Sleep efficiency (Percentage sleep: TST/time in bed)

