13.3.5 Sleep pattern

The patients' sleep pattern is evaluated using the CSHQ total score and by use of actigraphy.

An actigraph (ActiGraph GT9X Link) will be applied to the non-dominant wrist or ankle (9) and recordings will be made for 7 consecutive days and nights at Baseline and at Weeks 11 and 23. A daily wear time of 20 hours per day will be regarded as a compliant recording. The recording will be supported by an actigraph log, recorded in the eCRF.

The following parameters will be determined on the basis of recordings in the actigraph log:

- Bedtime (Clock time child is put to bed)
- Wake time (Clock time of child is taken out of bed)
- Time in bed (Time between Bedtime and Wake time)

The following variables are derived as obtained from the actigraph software:

- Sleep onset (Clock time for first appearance of a predetermined number of consecutive min of sleep)
- Sleep offset (Clock time for last of a predetermined number of consecutive min of sleep)
- Sleep period (Time between sleep onset and sleep offset)
- Total sleep time (TST, Duration of sleep in sleep period)
- Wake after sleep onset (WASO, number of minutes scored as wake during sleep period)
- Sleep efficiency (Percentage sleep: TST/time in bed)
- Night waking frequency (number of night wakings)
- Night waking duration (Sum of minutes scored as night waking)
- 24 h sleep duration (amount of sleep in a 24-h period)

Sleep onset latency is determined as Time between bedtime (as recorded on the actigraph log) and sleep onset (as captured by the actigraph software).

Changes from Baseline will be assessed at Week 12 and 24.

For more details regarding the methods used by the actigraph software please see the CSP for SOB003-001, Section 7.5.4.5.

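### At weekly dosing, the Week 12 and Week 24 actigraphy recordings contain one infusion day and night that baseline lacks, and SAP 13.3.5 has no rule for it

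*Protocol*

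**What the plan says.** **Recording.** SAP 13.3.5 says "recordings will be made for 7 consecutive days and nights at Baseline and at Weeks 11 and 23", and Protocol 7.5.4.5 says the same. The on-treatment start is fixed in Protocol 7.5.1.9 ("The parent/caregiver is instructed to start the sleep assessment 7 days prior to attendance for the 12th infusion") and 7.5.1.11 ("start the sleep assessment 7 days prior to attendance for the 24th infusion"). Protocol 7.5.4.5 aims to finish each on-treatment recording before the Week 12 or Week 24 infusion, and to secure that "at least 5 days of evaluable recordings are obtained on each occasion". A day counts as compliant with 20 hours of wear.

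**Dosing.** Protocol 7.4.6: "Every effort should be made to have the infusions administered every 7th day. A +/- 1-day window is applied after the 4th infusion". Its worked example for a first infusion on a Wednesday is that "the 5th to the 24th infusions can be administered on Tuesdays, Wednesdays or Thursdays".

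**Baseline conditions.** Protocol Table 3, footnote r: "Baseline assessment should preferably be completed prior to any anesthetic/sedation is applied and prior to PK and HS blood samplings".

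**Later change of window.** SAP Table 1, footnote r, lets the seven days fall anywhere in the two weeks before Weeks 12 and 24, and adds the aim that the child sleeps under usual conditions. SAP section 17 attributes the updated schedule tables to protocol clarification letters. SAP 13.3.5 was not changed to match and still gives Weeks 11 and 23.

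**Analysis.** SAP 13.3.5 takes change from baseline at Weeks 12 and 24. Neither document has a rule to exclude or flag an infusion day, or a summary without it.

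**The concern.** The comparison is between seven days with no infusion and, nominally, seven days with one. The infusion day is not an ordinary day. It brings antihistamine premedication, a 4-hour infusion with vital-sign checks, and a hospital stay of at least 12 hours from the start of infusion, which Protocol Table 1 allows to be extended. If a reaction occurs, the infusion may be prolonged up to 24 hours; Protocol 7.5.5.5 then requires hourly vital signs during it.

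Any of this could alter that day's or night's total sleep, latency, awakenings or wake after sleep onset. The study has no control group from which such an effect could be subtracted, and SAP 4.1 gives three patients in each of two cohorts. A reader of the summary table would have no way to tell a change in the child's usual sleep from the effect of one unusual day. The documents themselves lean towards keeping procedures out of the recording: baseline should come before sedation and sampling, and the on-treatment recording should end before the next infusion. The start instruction nonetheless brings in the previous infusion.

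**Working it through.** The plan gives no figure to reproduce, so the check is a count of calendar days. Put infusion 12 on day 0. The same counts apply to infusions 22 to 24.

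**1. Protocol rule, exact 7-day dosing.** Infusion 11 is on day -7. With attendance on the infusion day, the recording covers days -7 to -1 and includes day -7. With attendance the day before, it covers days -8 to -2 and still includes day -7.

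**2. SAP Table 1 window, exact 7-day dosing.** Infusions fall on days -14 and -7. A 7-day block ending before day 0 can start on any of days -14 to -7, which gives 8 blocks. The block starting on day -14 contains day -14, and the other seven contain day -7. None of the 8 is free. In hours, a full recording needs 7 x 24 = 168 h, while the time from the end of a 4-hour infusion to the next start is 168 - 4 = 164 h.

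**3. Protocol rule with the +/- 1-day window.** Each infusion may be at -1, 0 or +1 day from its nominal weekday. Gap between infusions 11 and 12 = 7 + (shift of 12) - (shift of 11).

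| Gap (days) | 5 | 6 | 7 | 8 | 9 |
|---|---|---|---|---|---|
| Combinations out of 9 | 1 | 2 | 3 | 2 | 1 |

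- Attendance on the infusion day: infusion 11 is inside when the gap is 7 or less, so 1 + 2 + 3 = 6 of 9.
- Attendance the day before: inside when the gap is 8 or less, so 6 + 2 = 8 of 9.

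**4. SAP window with the +/- 1-day window.** There are 27 combinations for infusions 10, 11 and 12. An infusion-free block exists when the gap from 11 to 12 is at least 8 days (9 combinations). It also exists when that gap is 7 or less but the gap from 10 to 11 is at least 8 (8 combinations). That makes 17 of 27; in the other 10 an infusion day is unavoidable.

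The counts in steps 3 and 4 are permitted schedules, not probabilities. Protocol 7.4.6 asks for every effort to keep to every seventh day, so the nominal case is the intended one.

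**5. Weight.** SAP 13.3.5 does not say how days are combined; I assume a simple mean over n evaluable days. A shift of d minutes on one day then moves the visit value by d/n. The documents give no value of d, so the table shows a range of assumed values.

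| Assumed shift d (min) | 15 | 30 | 60 | 120 |
|---|---|---|---|---|
| n = 7 (weight 1/7 = 14%) | 2.1 | 4.3 | 8.6 | 17.1 |
| n = 5, infusion day among them (weight 1/5 = 20%) | 3 | 6 | 12 | 24 |

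**6. After exclusion.** 7 - 1 = 6 days remain, against the aim of 5. If days are independent with equal variance (assumed), the within-child standard error of the visit mean rises by a factor of sqrt(7/6) = 1.08.

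**The case against.** Several points on the other side are sound.

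- **The overlap is not inevitable.** A reader might infer that every on-treatment recording must contain an infusion day. The documents do not support that: the +/- 1-day window permits gaps of 8 or 9 days, infusions may be postponed for infection, and the SAP window leaves room for an infusion-free block in 17 of 27 permitted schedules. What remains is that no text asks sites to choose such a block, and at exact 7-day dosing none exists.
- **The mechanism may be weak.** The antihistamine is specified as non-sedative. Infusions 11 and 23 require 12 hours in hospital, not a night. Corticosteroids and extra antihistamines depend on a reaction. The clean baseline is itself only an aim. A reader might infer a sizeable bias in the same direction in every child; nothing in the documents shows that. A disrupted day could shorten sleep in one child, and tiredness could lengthen it in another.
- **Infusion days are part of the regimen.** Treatment is weekly and expected to be life-long, so a week with one infusion describes sleep under treatment as given. This is a fair reading of the question, and a reason to keep the all-days summary beside the restricted one.
- **Little depends on it.** Actigraphy is exploratory and descriptive, the programme has been discontinued, six patients are analysed, and actigraphy and infusion data are listed by patient. That limits the importance of the point. It does not supply the missing rule, and the summary table would still show an unequal comparison without saying so.

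**Conclusion.** The point holds for the nominal weekly schedule. Each on-treatment recording then includes exactly one infusion day and night, baseline includes none, and SAP 13.3.5 neither excludes nor flags it. The reported sleep changes may therefore carry an infusion-day effect. Its weight is one day in seven, or one in five if only five days including that day are evaluable; its size and direction are unknown, and the minutes shown above rest entirely on assumed shifts. The conclusion also assumes that dosing stays close to every seventh day and that days are averaged with equal weight. It does not extend to a claim that the effect is always present or is known to distort the results. This is a minor but inexpensive improvement to an exploratory endpoint.

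**What to change.** 1. In SAP 13.3.5, summarise the Week 12 and Week 24 actigraphy variables excluding the calendar day of infusion and the night that follows. Identify the day by matching to the infusion dates that SAP 14.1 says are recorded in the eCRF. Present the all-days summary alongside, and mark the infusion day in the listing.
2. Exclude other in-hospital nights only if admission and discharge times are recorded; the documents do not show that they are.
3. State in SAP 13.3.5 how days are combined into a visit value, and carry over the protocol's aim of five evaluable days.
4. Reconcile the recording window. Protocol 7.5.4.5 and SAP 13.3.5 give Weeks 11 and 23, Protocol Table 3 footnote r gives Weeks 11-12 and 23-24, and SAP Table 1 footnote r gives the two weeks before Weeks 12 and 24.

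The cost is SAP wording, a date match and one extra summary. About one recording day per visit is lost from the restricted summary. That leaves about six at nominal dosing, with less margin if other days fail the 20-hour wear rule, and about five if a night in hospital before the infusion is also dropped. No new data are needed for items 1, 3 and 4. SAP 4.1 says that all six patients had already entered the extension study, so the remedy has to be in the analysis and not in how recordings are scheduled.

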7.5.1.12 Week 24 / last study visit

SOBI003 is administered as weekly infusions; a +/- 1-day window is applied. The patients will return to the hospital the day prior to or on the day of the last infusion. Adverse events and use of concomitant medications during non-hospital stay are captured. The actigraph and accompanying diary are collected.

Prior to start of the infusion, the following is performed:

- Vital signs and a 12-lead ECG is obtained
- General appearance and skin are assessed
- Blood is obtained for immunogenicity, HS and PK assessments
- Urine is collected for HS analysis

Within 30 to 60 minutes prior to start of each SOBI003 infusion, a single dose of an oral non-sedative antihistamine is administered. SOBI003 is administered in accordance with Section 7.4.6.

Vital signs are assessed approximately 2 hours after start of infusion. Upon completion of the 4-hour infusion, and as soon as practically possible, a PK blood sample is obtained. Within an hour of completion of the infusion, vital signs and general appearance and skin are assessed, and a 12-lead ECG is obtained.

The parent/caregiver completes the CSHQ questionnaires, preferably during Day 1.

On Day 2, blood is collected for HS and PK assessment at the same time point as CSF sampling is performed. Urine is collected for HS analyses as close as possible to the CSF sampling. General anesthesia is applied in accordance with local routines at the study site. CSF sampling (a total of 0,9 mL) for PK, ADA, and HS assessments and MRI scanning of brain, liver and spleen are completed while the patient is anesthetized. The order of the procedures should preferably be as stated. Should this not be feasible for an individual patient, then effort should be made to have the assessments performed in the same order as they were performed at Baseline. When separate consent for future research has been provided, CSF (1.0 mL) will also be collected for storage at the central laboratory.

On Day 3, blood and urine are collected for safety laboratory analyses. Blood is also collected for PK analysis. Vital signs are obtained. The VABS-II is assessed by interviewing the parent/caregiver (refer to Section 7.5.4.1).

In addition, PK blood samples are collected on Days 5, 6 and 8 (approximately 168h after start of SOBI003 infusion) at time points specified in Section 7.5.6.1.

The parent/caregiver completes the PedsQL questionnaire, preferably during Day 6.

Based on the patient's developmental age, as determined by the VABS-II score, the BSID-III and/or KABC-II tests are conducted for assessment of neurocognition, language and motor function (see Sections 7.5.4.2, 7.5.4.3, and 7.5.4.4, respectively). If *only* BSID-III or *only* KABC-II is to be assessed, then this should be done on Day 7. If *both* BSID-III and KABC-II should be assessed, then the BSID-III should be administered on Day 4 or 5 and the KABC-II on Day 7.

On Day 7, a neurological and a physical examination are performed and height, weight and head circumference are obtained. A 12-lead ECG and echocardiography are performed. Should Day 7 not be practically feasible, then the ECG and echocardiography can be performed during Days 3 to 7.

The patient may be discharged from the hospital 48 hours after start of the infusion. The patient will then return to the hospital for study assessments on Days 4, 5, 6 and 7.

On Day 7, height, weight and head circumference are assessed and the investigator will assess patient eligibility for enrolment in the extension study SOBI003-002.

For patients that are permanently discontinuing SOBI003 treatment, i.e., not continuing in the extension study, serum samples for PK and ADA analyses should be obtained 30 to 40 days after last SOBI003 infusion. Patients with ADA-positive samples should continue to be followed in accordance with Sections 7.5.5.3 and 7.5.6.1.

